10. Cycle cancellation is defined generally as a cycle in which ovarian stimulation or monitoring has been initiated with the intention to treat, but which did not proceed to follicular aspiration or, in the case of a thawed or warmed embryo, did not proceed to embryo transfer. Information on cycle cancellation will be ascertained in the IVF registers.
11. Ovarian hyperstimulation syndrome is defined generally as an exaggerated systemic response to COS characterized by a wide spectrum of clinical and laboratory manifestations. It will be ascertained in this study based on a recorded primary or secondary diagnosis of OHSS within inpatient or outpatient specialized care within 70 days (10 weeks) after oocyte retrieval or as recorded in the IVF registers in a given IVF/ICSI stimulation cycle. For descriptive purposes, OHSS will be classified as early if it occurred within 9 days after oocyte retrieval, and late if it occurred 10 or more days after oocyte retrieval. The day of hospital admission (inpatient care) or hospital visit (outpatient care) will be defined as the onset of OHSS (23). A woman may experience both early and late OHSS. Thus, for the description of OHSS, a woman may be counted towards the early and late classification in a given cycle. For the combined measure to be used in the comparative analyses, only one occurrence of OHSS per cycle will be counted. If a new cycle was initiated within 70 days after oocyte retrieval, the previous stimulation cycle will be excluded from further descriptive and comparative analyses with respect to OHSS from the date of treatment start for the new cycle. The diagnosis code used to ascertain OHSS is provided in Appendix 3 (Section 14.3.1).
12. Treatment-associated costs are defined as direct medical costs of treatments (drugs and other treatments), pregnancy loss/birth, and adverse events (*i.e.*, OHSS) resulting from an IVF/ICSI stimulation cycle.

Detailed definitions for ascertainment of the secondary outcomes using ICD-10 and procedure codes, as applicable, are provided in Appendix 3 (Section 14.3.1). For the calculation of the secondary outcome measures, refer to Section 9.7.3.3 (Table 7).

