9.7.1 Analysis Sets

To address the study objectives, analysis sets will be constructed based on the study outcomes as defined in Section 9.1.2. To allow for a sufficient time period to assess the outcomes after the initiation of a stimulation cycle, the analysis sets will be restricted to outcome-specific time periods. For the analysis sets, the following outcome-specific time periods are applied: 1 year after the stimulation cycle initiation for LBR, CPR, OPR, MC-CLBR and TTLB; 1 year after the stimulation cycle and linked FET initiation for CLBR, CCPR, COPR, pregnancy loss, multiple pregnancy and treatment-associated costs; 1.5 months after the stimulation cycle initiation for oocyte retrieval and embryos cryopreserved per initiated stimulation cycle, and cycle cancellation; 1 month after the stimulation cycle aspiration for oocyte retrieval and embryos cryopreserved per aspirated stimulation cycle; 4 months after stimulation cycle initiation for OHSS; 3 months after last embryo transfer for implantation. Fresh and frozen embryo transfers will be assessed by using all fresh and frozen embryo transfers done by the end of the study period (31 December 2020).

The analysis sets and their use for the study objectives and outcomes are defined in Table 5. The use of analysis sets will be described in the statistical analysis, and any needed specific modifications or restrictions on the analysis sets needed for the analysis of the study objectives will be further described in the SAP.

Table 5. Description of analysis sets

Analysis set	Description of the analysis set	Study objective(s)	Study outcome measure(s)
Set 1	Stimulation cycles with drug of interest initiated on or before 31 December 2019	Primary objective	LBR
		Secondary objective 1	CPR
			OPR
Set 2	Stimulation cycles with drug of interest and linked FET cycles initiated on or before 31 December 2019	Primary objective	CLBR
		Secondary objective 1	CCPR
			COPR
		Secondary objective 5	Pregnancy loss
		Secondary objective 6	Multiple pregnancy
Secondary objective 9	Treatment-associated costs		
Set 3	Stimulation cycles with drug of interest initiated on or before 15 November 2020 ⁺	Secondary objective 2	Oocytes retrieved per initiated stimulation cycle
			Embryos cryopreserved per initiated stimulation cycle
			Utilizable embryos per initiated stimulation cycle
		Secondary objective 7	Cycle cancellation

Analysis set	Description of the analysis set	Study objective(s)	Study outcome measure(s)

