		Per aspirated stimulation cycle	Set 4	Number (see section 9.7.3.3)

Study objective	Outcome	Unit of analysis	Analysis set	Analysis results
				Adjusted OR (see section 9.7.3.4) Stratified analysis (see section 9.7.3.6)
	Number of embryos transferred	Per fresh embryo transfer	Set 6	Number (see section 9.7.3.3) Adjusted OR (see section 9.7.3.4)
		Per frozen embryo transfer	Set 6	Number (see section 9.7.3.3) Adjusted OR (see section 9.7.3.4)
	Number of embryos cryopreserved	Per initiated stimulation cycle	Set 3	Number (see section 9.7.3.3) Adjusted OR (see section 9.7.3.4)
		Per aspirated stimulation cycle	Set 4	Number (see section 9.7.3.3) Adjusted OR (see section 9.7.3.4)
	Number of utilizable embryos	Per initiated stimulation cycle	Set 3	Number (see section 9.7.3.3) Adjusted OR (see section 9.7.3.4)
		Per aspirated stimulation cycle	Set 4	Number (see section 9.7.3.3) Adjusted OR (see section 9.7.3.4)
Secondary objective 3	Implantation rate	Per embryos transferred per stimulation cycle	Set 7	Rate (see section 9.7.3.3) Adjusted OR (see section 9.7.3.4)
Secondary objective 4	Time-to-live birth	Per woman per up to five stimulation cycles with the same drug	Set 8	Kaplan-Meier plots and estimates (see section 9.7.3.5) Adjusted live birth rate ratios (see section 9.7.3.5)
Secondary objective 5	Rate of pregnancy loss	Per clinical pregnancy following embryo transfer	Set 2	Rate (see section 9.7.3.3) Adjusted OR (see section 9.7.3.4)
Secondary objective 6	Multiple pregnancy rate	Per clinical pregnancy following embryo transfer	Set 2	Rate (see section 9.7.3.3) Adjusted OR (see section 9.7.3.4)

Study objective	Outcome	Unit of analysis	Analysis set	Analysis results
Secondary objective 7	Cycle cancellation rate	Per initiated stimulation cycle	Set 3	Rate (see section 9.7.3.3) Adjusted OR (see section 9.7.3.4)
Secondary objective 8	OHSS rate	Per initiated stimulation cycle	Set 5	Rate (see section 9.7.3.3) Adjusted OR (see section 9.7.3.4)
Secondary objective 9	Treatment-associated costs	Per initiated stimulation cycle	Set 2	Descriptive cost analysis (see section 9.7.3.7)

CCPR: cumulative clinical pregnancy rate; CLBR: cumulative live birth rate; CPR: clinical pregnancy rate; COPR: cumulative ongoing pregnancy rate; LBR: live birth rate; MC-CLBR: multiple-cycle cumulative live birth rate; OPR: ongoing pregnancy rate; OHSS: ovarian hyperstimulation syndrome; OR: odds ratio.

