Secondary objective 1	CPR	Number of clinical pregnancies after fresh embryo transfer	Initiated cycles with drug of interest
	CCPR	Number of clinical pregnancies after one initiated stimulation cycle, including all fresh or frozen embryo transfers linked to that cycle	Initiated cycles with drug of interest
	OPR	Number of ongoing pregnancies after fresh embryo transfer	Initiated cycles with drug of interest
	COPR	Number of ongoing pregnancies after one initiated stimulation cycle, including all fresh or frozen embryo transfers linked to that cycle	Initiated cycles with drug of interest
Secondary objective 2	Number of oocytes retrieved	Number of oocytes retrieved	Initiated cycles with drug of interest
		Number of oocytes retrieved	Aspirated cycles with drug of interest

Study objective	Outcome measure	Numerator	Denominator
	Number of embryos transferred	Number of fresh embryos transferred	Fresh embryo transfers linked to cycles with drug of interest
		Number of frozen embryos transferred	Frozen embryo transfers linked to cycles with drug of interest
	Number of embryos cryopreserved	Number of embryos cryopreserved	Initiated cycles with drug of interest
		Number of embryos cryopreserved	Aspirated cycles with drug of interest
	Number of utilizable embryos	Number of utilizable embryos	Initiated cycles with drug of interest
		Number of utilizable embryos	Aspirated cycles with drug of interest
Secondary objective 3	Implantation rate	Number of intrauterine gestational sacs after one fresh or frozen embryo transfer	Number of embryos transferred in one cycle
Secondary objective 4	TTLB	Time to first delivery with at least one live birth in up to five stimulation cycles with the same study drug, including all fresh or frozen embryo transfers linked to each of those stimulation cycles	N/A; conducted as time-to-event analysis; unit of analysis is women who initiated stimulation cycles with drug of interest
Secondary objective 5	Rate of pregnancy loss	Number of induced and spontaneous abortions	Clinical pregnancies with drug of interest following fresh or frozen embryo transfer
Secondary objective 6	Multiple pregnancy rate	Number of multiple pregnancies	Clinical pregnancies with drug of interest following fresh or

Study objective	Outcome measure	Numerator	Denominator
			frozen embryo transfer
Secondary objective 7	Cycle cancellation rate	Number of canceled cycles	Initiated cycles with drug of interest, including any linked initiated FET cycles

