9.7.3.4 Adjusted Odds Ratios

For the comparison of the study cohorts, the ORs (with 95% CI), adjusted for confounding factors, will be estimated by taking into account the IPTWs and using statistical modelling, such as regression analysis or general estimating equations. To estimate the adjusted ORs, the statistical model will be weighted with IPTWs and will include as covariates any variables that were used in the PS but are still unbalanced between the study cohorts after weighting. Statistical models may also be used to additionally adjust the ORs for any other potential covariates that are assessed after the initiation of the IVF/ICSI stimulation cycle and hypothesized to be associated with the given study outcomes (see Table 1 in Section 9.3.2).

For the statistical models, the following study outcomes will be considered as binary outcomes analyzed per fresh embryo transfer: live birth (*i.e.*, a primary objective outcome), clinical pregnancy and ongoing pregnancy (*i.e.*, a subset of secondary objective 1 outcomes). For the statistical models, the following study outcomes will be considered as binary outcomes analyzed per woman: MC-CLBR (*i.e.*, a primary objective outcome) will be analyzed as a binary outcome per woman in statistical models.

For the statistical models, the following study outcomes will be considered as binary outcomes analyzed per clinical pregnancies following fresh or frozen embryo transfer: pregnancy loss (secondary objective 5) and multiple pregnancy (secondary objective 6). Cycle cancellation (secondary objective 7) and OHSS occurrence (secondary objective 8) will be analyzed as binary outcomes per initiated stimulation cycle. Implantation (secondary objective 3) will be analyzed as an ordinal categorical outcome per fresh or frozen embryo transfer.

For the statistical models, the following study outcomes are considered as counts analyzed per initiated stimulation cycle: cumulative live birth (*i.e.*, a primary objective outcome), cumulative clinical pregnancy and cumulative ongoing clinical pregnancy (*i.e.*, a subset of secondary objective 1 outcomes). Also the following study outcomes are considered as counts in statistical models and

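### Cycle cancellation has two incompatible units: Table 7 counts linked FET cycles, while Table 6, Set 3, the follow-up window and the model use stimulation cycles

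*Protocol*

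**What the plan says.** Two groups of statements in the Protocol apply to the same outcome.

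**Stimulation plus FET cycles**
- Section 9.1.2.2 defines cancellation as a started cycle that does not reach follicular aspiration or, "in the case of a thawed or warmed embryo, did not proceed to embryo transfer".
- Table 7 (Section 9.7.3.3) gives the numerator as "Number of canceled cycles", without stating the type of cycle, and the denominator as "Initiated cycles with drug of interest, including any linked initiated FET cycles". Section 9.7.3.3 says that outcome measures are calculated by the Table 7 definitions, so this cell governs the reported rate.

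**Stimulation cycles**
- Section 8.2 words secondary objective 7 in terms of IVF/ICSI stimulation cycles.
- Table 6 (Section 9.7.3) lists the cancellation rate and its adjusted OR with the unit "Per initiated stimulation cycle" on Set 3.
- Table 5 (Section 9.7.1) defines Set 3 as "Stimulation cycles with drug of interest initiated on or before 15 November 2020".
- Section 9.7.1 sets the follow-up as "1.5 months after the stimulation cycle initiation for oocyte retrieval and embryos cryopreserved per initiated stimulation cycle, and cycle cancellation".
- Section 9.7.3.4 states: "Cycle cancellation (secondary objective 7) and OHSS occurrence (secondary objective 8) will be analyzed as binary outcomes per initiated stimulation cycle".

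**The concern.** Section 8.2 classes objectives 5 to 8 as treatment safety. For objective 7 a reader would see a rate per cohort and an adjusted OR side by side and expect them to describe one event in one population. As written they do not, and Tables 6 and 7 disagree about the rate itself.

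The choice of unit also matters for comparing drugs. Linked FET cycles arise after exposure and only when stimulation has yielded embryos to freeze. A denominator that includes them responds to embryo yield, which the study compares in its own right under secondary objective 2. Weighting on baseline covariates does not remove a difference that arises after treatment starts. Two cohorts with identical cancellation risks could therefore show different rates.

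**Working it through.** The protocol states no figure for cancellation, so there is nothing to reproduce. The check is a comparison of the text, followed by an illustration with assumed inputs.

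**1. Can the Table 7 rate be computed on Set 3?** Set 3 contains stimulation cycles and names no FET cycles. The omission looks deliberate, because the protocol names FET cycles where it wants them. Set 2 is "Stimulation cycles with drug of interest and linked FET cycles initiated on or before 31 December 2019", and cancellation is not assigned to it. The 1.5-month window runs from the start of stimulation, so linked FET cycles started later fall outside it. Among the Table 7 rows that divide by initiated cycles, cancellation is the only one that adds FET cycles. The answer is no.

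**2. Do the rate and the OR share a unit?** The rate divides by stimulation plus FET cycles; the OR is modelled per initiated stimulation cycle. The protocol does not say how a cancelled FET cycle enters the binary outcome of its stimulation cycle. The answer is again no.

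**3. How far can the Table 7 rate move without a drug effect?** Let s be the cancellation probability per stimulation cycle, f the probability per FET cycle and m the linked FET cycles per stimulation cycle.

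Table 7 rate = (s + f·m) / (1 + m)

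Hold s and f equal in both cohorts and let only m differ. All values of s, f and m are assumptions.

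| s | f | m (A vs B) | Rate A | Rate B | Implied OR |
|---|---|---|---|---|---|
| 10% | 2% | 0.9 vs 0.6 | 0.118/1.9 = 6.21% | 0.112/1.6 = 7.00% | 0.88 |
| 10% | 5% | 0.9 vs 0.6 | 0.145/1.9 = 7.63% | 0.130/1.6 = 8.125% | 0.93 |
| 10% | 10% | 0.9 vs 0.6 | 0.190/1.9 = 10.0% | 0.160/1.6 = 10.0% | 1.00 |
| 5% | 10% | 0.9 vs 0.6 | 0.140/1.9 = 7.37% | 0.110/1.6 = 6.875% | 1.08 |
| 15% | 2% | 1.0 vs 0.5 | 0.170/2.0 = 8.50% | 0.160/1.5 = 10.67% | 0.78 |
| 5% | 10% | 1.0 vs 0.5 | 0.150/2.0 = 7.50% | 0.100/1.5 = 6.67% | 1.14 |

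The last two rows are the extremes over s = 5, 10, 15%, f = 2, 5, 10% and m = 0.6/0.5, 0.9/0.6, 1.0/0.5. Counting only stimulation-cycle cancellations per stimulation cycle gives s in both cohorts and an OR of 1.00 in every row.

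**4. A smaller contrast tied to the protocol.** Section 7 cites trials of the reference product against hMG with mean oocytes of 12.29 vs 9.67, 14.4 vs 11.3 and 11.8 vs 10.0, which are ratios of 1.27, 1.27 and 1.18. Assume that FET counts scale with oocytes, with m = 1.0 for the reference product, s = 10% and f = 2%.
- m = 11.3/14.4 = 0.785 for hMG: 6.00% vs 6.48%, implied OR 0.92.
- m = 10.0/11.8 = 0.847 for hMG: 6.00% vs 6.33%, implied OR 0.94.

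For biosimilars the protocol gives no yield difference to use.

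**5. The alternative reading of the model.** Suppose the outcome per stimulation cycle means any cancellation in that cycle or its linked FET cycles. Taking FET cancellations as independent, its probability is 1 − (1 − s)(1 − f)^m. With s = 10%, f = 5% and m = 0.9 vs 0.6 this gives 14.06% vs 12.73%, OR 1.12. This outcome also depends on the FET count, and it still differs from the Table 7 rates in row 2.

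**The case against.** The strongest reply is that this is a wording slip. Objective 7, Table 6, Set 3 and Section 9.7.3.4 all point to stimulation cycles, the outcome is one of nine secondary objectives, and Section 9.7.1 leaves modifications of analysis sets to the SAP. It is true that the primary objective, the study size and the cohorts are untouched. But an SAP can add detail only where the protocol is open. Here the protocol fixes both versions, and Section 9.7.3.3 tells the analyst to follow Table 7.

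Two stronger readings are tempting, and the documents support neither.

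- A reader might infer that the Table 7 rate favours whichever drug yields more embryos. That holds only if FET cycles are cancelled less often than stimulation cycles. With equal probabilities there is no effect, and with more frequent FET cancellation the direction reverses. The protocol gives neither probability.
- A reader might infer that the between-drug safety comparison is biased. The planned comparison is the adjusted OR per initiated stimulation cycle. The implied ORs in the working come from the Table 7 rates; the plan does not estimate them.

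It is also fair to say that a combined measure of stimulation and FET cancellation could be a legitimate choice. It would then need its own set, window and model.

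**Conclusion.** The point holds as an internal contradiction that should be resolved before analysis. The definition and Table 7 count linked FET cycles; Table 6, Set 3, the window and Section 9.7.3.4 do not. This conclusion rests on the text alone and needs no assumed number.

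The possible distortion of the reported rate is conditional. It requires different cancellation probabilities for stimulation and FET cycles and different FET counts between cohorts. The implied OR range of about 0.78 to 1.14 depends wholly on the assumed inputs. With FET contrasts scaled to the cited hMG oocyte means it was 0.92 to 0.94, under one assumed pair of cancellation probabilities. The effect is confined to one secondary safety objective.

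**What to change.** Use one unit for both the rate and the adjusted OR: stimulation cycles cancelled before follicular aspiration, divided by initiated stimulation cycles, on Set 3 with its 1.5-month window. Four places need to agree.

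- **Section 9.1.2.2:** limit the objective 7 outcome to cancellation before aspiration, and define FET cycles not reaching transfer as a separate descriptive measure.
- **Table 7:** change the numerator to stimulation cycles cancelled before aspiration, and delete the FET addition from the denominator.
- **Table 6:** keep the unit and Set 3 for the main measure, and add a row for the FET measure.
- **Section 9.7.3.4:** state that a cancelled FET cycle does not count as an event for its stimulation cycle.

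Report FET cycles not reaching transfer per initiated linked FET cycle, descriptively. This measure needs a named analysis set and a follow-up window in Section 9.7.1 that include FET cycles, because Set 3 cannot supply them. Correcting the Table 7 cell alone would leave the definition in conflict and the FET measure without a population.

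The cost is a few lines of text and one extra descriptive row.

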9.7.3.4 Adjusted Odds Ratios

For the comparison of the study cohorts, the ORs (with 95% CI), adjusted for confounding factors, will be estimated by taking into account the IPTWs and using statistical modelling, such as regression analysis or general estimating equations. To estimate the adjusted ORs, the statistical model will be weighted with IPTWs and will include as covariates any variables that were used in the PS but are still unbalanced between the study cohorts after weighting. Statistical models may also be used to additionally adjust the ORs for any other potential covariates that are assessed after the initiation of the IVF/ICSI stimulation cycle and hypothesized to be associated with the given study outcomes (see Table 1 in Section 9.3.2).

For the statistical models, the following study outcomes will be considered as binary outcomes analyzed per fresh embryo transfer: live birth (*i.e.*, a primary objective outcome), clinical pregnancy and ongoing pregnancy (*i.e.*, a subset of secondary objective 1 outcomes). For the statistical models, the following study outcomes will be considered as binary outcomes analyzed per woman: MC-CLBR (*i.e.*, a primary objective outcome) will be analyzed as a binary outcome per woman in statistical models.

For the statistical models, the following study outcomes will be considered as binary outcomes analyzed per clinical pregnancies following fresh or frozen embryo transfer: pregnancy loss (secondary objective 5) and multiple pregnancy (secondary objective 6). Cycle cancellation (secondary objective 7) and OHSS occurrence (secondary objective 8) will be analyzed as binary outcomes per initiated stimulation cycle. Implantation (secondary objective 3) will be analyzed as an ordinal categorical outcome per fresh or frozen embryo transfer.

For the statistical models, the following study outcomes are considered as counts analyzed per initiated stimulation cycle: cumulative live birth (*i.e.*, a primary objective outcome), cumulative clinical pregnancy and cumulative ongoing clinical pregnancy (*i.e.*, a subset of secondary objective 1 outcomes). Also the following study outcomes are considered as counts in statistical models and

will be analyzed both per initiated stimulation cycle and per aspirated stimulation cycle: number of oocytes retrieved and number of utilizable embryos (*i.e.*, a subset of secondary objective 2 outcomes). Number of embryos transferred (*i.e.*, a secondary objective 2 outcome) will also be considered as a count outcome in statistical models and will be analyzed per fresh and frozen embryo transfers. For modelling the count data appropriately, the distribution of count data will be checked by counting the mean and the variance of the data and the possibility of excess zeros in the count data will be evaluated visually by plotting the distribution of the data.

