9.3.2 Other Variables (Covariates)

In addition to the outcome and exposure variables outlined in Section 9.1.2 and Section 9.3.1, the covariates of interest in this study are listed below and classified according to their intended use in the analysis (Table 1).

The variables are generally described as measured in relation to each IVF/ICSI stimulation cycle; however, variables used to derive the outcome variables may also apply to any linked FET cycles, depending on the outcome under study. Variables indicated as being candidates for regression modeling are determined after the decision on which gonadotropin to use for COS has been made. These variables will therefore not be included in the PS but may instead be added as independent covariates in the IPTW-weighted regression model (see Section 9.7.3.1 for further details).

For variables identified in the registers by ATC, ICD-10 and/or procedure codes, these operational definitions are provided in Appendix 3 (Section 14.3.3).

Table 1. List of covariates and their use in the study

Variable	Measurement scale	Baseline characteristic	Candidate variable for PS	Candidate variable for additional adjustment
Demographic characteristics				
Age at stimulation cycle index date	Continuous	X	X	
IVF/ICSI treatment characteristics				
Treatment type (ICSI, IVF, ICSI + IVF; FET)	Categorical	X	X	
Type of clinic (private, public)	Categorical	X	X	
Calendar year of stimulation cycle	Continuous	X		
GnRH protocol (agonist, antagonist)	Categorical	X	X	
Cycle cancellation (timing within cycle)	Categorical	N/A (used to derive outcome variable)		
Date of cycle cancellation	Continuous	N/A (used to derive outcome variable)		
Type of drug for ovulation triggering	Categorical	X		X

Variable	Measurement scale	Baseline characteristic	Candidate variable for PS	Candidate variable for additional adjustment
Type of drug for luteal phase support	Categorical	X		X
Date of follicular aspiration	Continuous	N/A (used to derive outcome variable)		
Date of embryo transfer	Continuous	N/A (used to derive outcome variable)		
Number of days of embryo cultivation ⁺	Numerical	X		X
Date of embryo cryopreservation	Continuous	N/A (used to derive outcome variable)		
Embryo cryopreservation method (slow freezing, vitrification)	Categorical	X		X
Date of embryo thawing	Continuous	N/A (used to derive outcome variable)		
Number of embryos thawed	Continuous	N/A (used to derive outcome variable)		

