9.7.3.5 Time-to-Live Birth Analysis

TTLB (secondary objective 4) will be analyzed restricting to women who initiated their first-ever stimulation cycle during the study period. As per study design, only the first five stimulation cycles (including all cycles of fresh or frozen embryo transfers) with the same study drug will be considered. The stimulation cycle rank number will be employed as the unit of time. Women will be followed until the first delivery with at least one live birth linked to treatment with the drug of interest, the sixth stimulation cycle, switch to another drug used for COS, diagnosis of breast, ovarian or uterine cancer, death, emigration (Denmark only) or end of study, whichever occurs first.

To estimate the TTLB in the original and IPTW-weighted study cohorts, survival analysis will be performed with the Kaplan-Meier method to estimate the time to the first live birth, expressed as the rank number of the stimulation cycle with the given study drug. The resulting Kaplan-Meier plots together with the estimated mean (with 95% CI) and median (with 95% CI) time-to-events will be presented.

For the comparison of the study cohorts, the time-to-live birth rate ratios adjusted for confounding factors, will be estimated by taking into account the IPTWs and using Cox proportional hazards regression model. The Cox model will be weighted with the IPTWs, and any variables included in the PS that are still unbalanced after weighting will be included as covariates for the Cox model. Additionally, the Cox model may be used to adjust the rate ratios for any other potential covariates that are assessed after the start of the stimulation cycle and hypothesized to be associated with the given study outcomes (see Table 1 in Section 9.3.2).

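### Sections 9.7.3.4 and 9.7.3.5 let the primary odds ratios and the time-to-live-birth rate ratios be adjusted for variables fixed after the gonadotropin is chosen, which can remove part of the product effect or introduce bias

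*Protocol*

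**What the plan says.** The main model for the adjusted ORs (Section 9.7.3.4) is weighted by IPTW and includes any propensity-score (PS) variables still unbalanced after weighting. The section then gives the analyst the option to "additionally adjust the ORs for any other potential covariates that are assessed after the initiation of the IVF/ICSI stimulation cycle", provided these are hypothesised to be associated with the outcome, and it refers to Table 1. The permission covers all outcomes modelled in that section, including live birth. Section 9.7.3.5 does the same for TTLB: the Cox model may "adjust the rate ratios for any other potential covariates that are assessed after the start of the stimulation cycle".

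Section 9.3.2 explains how these candidates were chosen: "Variables indicated as being candidates for regression modeling are determined after the decision on which gonadotropin to use for COS has been made". It continues: "These variables will therefore not be included in the PS but may instead be added as independent covariates in the IPTW-weighted regression model". The last column of Table 1 marks four of them:

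- "Type of drug for ovulation triggering"
- type of drug for luteal phase support
- "Number of days of embryo cultivation"
- embryo cryopreservation method

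The target is set elsewhere. Section 9.7.3 describes estimating the effect of the reference product on the live birth rates, and Section 9.7.3.1 says that IPTW gives the treatment effect in the overall population. No direct effect is defined.

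**The concern.** The reason given for keeping these variables out of the PS is that they come after the treatment decision. The same reason argues against putting them in the outcome model when the aim is a total effect. A variable on the path from product to live birth carries part of the effect, and holding it constant removes that part. If the variable also shares an unmeasured cause with live birth, holding it constant links product to that cause and can produce an association where none exists.

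Association with the outcome does not guard against this, because a mediator is associated with the outcome by construction. At stake is whether a reported adjusted OR answers the question in Section 8, namely which product gives better results, or a different and undefined question.

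**Working it through.** **1. The passages side by side.**

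| Element | Where | Content |
|---|---|---|
| Target | 9.7.3, 9.7.3.1 | Effect of the product in the overall population |
| Timing of the four variables | 9.3.2 | They "are determined after the decision on which gonadotropin to use for COS has been made" |
| Permitted use | 9.3.2, 9.7.3.4, 9.7.3.5 | Optional covariates in the weighted outcome models |
| Selection rule | 9.7.3.4, 9.7.3.5 | Hypothesised association with the outcome |
| Product to ovarian response | Section 7 | Cited trials found more oocytes with the reference product than with hMG |
| Response to outcome | Table 8, analysis 4 | Oocyte yield is positively associated with CLBR |
| Unmeasured common cause | 9.9.4, Table 1 notes | Antral follicle count and anti-Müllerian hormone are unavailable in Sweden and likely partial in Denmark; Danish laboratory values are for a sensitivity analysis only |

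The protocol therefore supplies a plausible route (product, response, later steps of the cycle, live birth) and acknowledges that a likely common cause is largely unmeasured. It does not quantify an effect of product on any of the four variables. It keeps oocyte yield, also a post-start variable, out of the main analysis and examines it only in a sensitivity analysis. The four Table 1 variables have no such restriction.

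**2. What adjustment can do.** The protocol has no figure to reproduce here. The mechanism was simulated with 2,000,000 cycles per scenario, where A is product, M a binary post-start variable, Y live birth and U unmeasured prognosis (standard normal):

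- logit P(M) = −0.2 + a·A + u·U
- logit P(Y) = −1.1 + d·A + m·M + v·U

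Every coefficient is an assumption.

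| Scenario | a | u | d | m | v | Total OR | OR adjusted for M |
|---|---|---|---|---|---|---|---|
| Effect wholly through M | 0.4 | 0 | 0 | 0.6 | 0 | 1.056 | 0.994 |
| Direct plus mediated | 0.4 | 0 | 0.05 | 0.6 | 0 | 1.115 | 1.053 |
| True null, M shares a cause with Y | 0.4 | 1.0 | 0 | 0 | 0.7 | 1.001 | 0.957 |
| Effect through M, shared cause | 0.4 | 1.0 | 0 | 0.6 | 0.7 | 1.050 | 0.960 |
| Product does not affect M | 0 | 1.0 | 0.1 | 0.6 | 0.7 | 1.090 | 1.097 |

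The Monte Carlo standard error of a log OR is about √(2 / (1,000,000 × 0.31 × 0.69)) = 0.003. The 0.994 in row 1 is therefore compatible with its constructed value of 1. Row 3 is pure collider bias. Swapping the cohort labels in row 3 gives 1/0.957 = 1.045, so the sign depends on which product raises M. Row 5 shows only the small change from non-collapsibility of the OR.

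**3. Scale.** Section 9.5 takes a comparator MC-CLBR of 50% and detectable differences of 1.5 to 2.5 percentage points. As ORs these are (0.515/0.485)/(0.50/0.50) = 1.062 and (0.525/0.475)/(0.50/0.50) = 1.105. Shifts of the size in rows 1 to 4 would be comparable with the effects the study is meant to detect, if the assumed coefficients were realistic.

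**The case against.** **The adjustment is optional and the core model is fixed.** This is right. The IPTW model with unbalanced PS variables is stated firmly, and post-start covariates come under a permission. A reader might infer that the choice will be made after results are seen. The documents do not support that, because Sections 9.7 and 9.7.3 defer details to an SAP that is not at hand. What stands is that the protocol expressly grants the permission for the primary outcomes without saying which model is the main one.

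**No product effect on the four variables is shown.** This is also right. Appendix Section 14.3.3 lists only two hCG preparations as trigger drugs and only progesterone for luteal support, so variation driven by ovarian response is not evident from those codes. Section 9.1.1 presents vitrification and blastocyst transfer as trends over calendar time. Bias is possible, not demonstrated.

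**A stronger reading is tempting.** Culture days and cryopreservation method exist only when there are embryos. A reader might infer that the missing-data category of Section 9.7.2 would then collect cycles in which live birth is impossible, so that adjustment erases any effect through embryo yield. The documents do not support this:

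- Section 9.7.2 says that variables recorded only when an event occurs are not treated as missing.
- A cycle with a fresh transfer and nothing frozen has no cryopreservation method but can give a live birth. A cycle with all embryos frozen has no fresh-transfer date but can contribute to CLBR.
- Section 9.7.3.4 models live birth per fresh embryo transfer, so cycles without embryos are not units in that model. (Table 6 gives a different unit, which is a separate matter.)

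**Striking the permission for every outcome would go too far.** Agreed. It also covers outcomes analysed per pregnancy or per transfer, where the problem shown here does not require deletion.

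**Conclusion.** The point holds in a limited form. The protocol allows the primary live-birth ORs and the TTLB rate ratios to be adjusted for variables it describes as later than the treatment choice, under a rule that does not exclude mediators, while aiming at a total effect. That is an inconsistency in the text and does not depend on the simulation.

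Whether an adjusted estimate would be biased depends on two conditions: that the product influences at least one of the four variables, and, for collider bias, that an unmeasured factor such as ovarian reserve affects both that variable and live birth. The first is plausible from the protocol's background but unquantified. The second is made likely by Section 9.9.4. The size cannot be derived from the documents. The simulated shifts, about 4% to 9% in the OR when the product affects the variable and under 1% when it does not, show direction and order of magnitude under assumed coefficients only. Section 9.9 does not discuss this risk. The change should be made.

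**What to change.** - In Sections 9.7.3.4 and 9.7.3.5, state that the main ORs for LBR, CLBR and MC-CLBR and the main TTLB rate ratios use IPTW plus only those baseline PS variables still unbalanced after weighting.
- State that any model of these outcomes with post-start covariates is supportive or exploratory and does not estimate the total effect of the product. Add the same note to the additional-adjustment column of Table 1.
- If the motive is the change in cryopreservation and culture practice described in Section 9.1.1, address it with a pre-treatment variable: add calendar year to the PS. Table 1 lists it as a baseline characteristic but does not mark it for the PS. Section 9.9.2 notes that biosimilar use rose over the study period, so year is related to exposure as well.

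The cost is two or three sentences, a table note and one mark in Table 1, with no new data and no loss of cycles from restricting the covariates. Calendar year may produce some large weights where a product was rare in a given year; the weight checks in Section 9.7.3.1 already cover that.
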